11.2.2 Safety and Tolerability

11.2.2.1 Subject Adherence

Number of treatment cycles per subject will be summarized by numbers and percents of subjects who received each number of treatment cycles.

11.2.2.2 Concurrent Medications

Number and percent of subjects in the FAS and in the PPS who took each individual concurrent medication and each class of concurrent medication will be provided.

11.2.2.3 Safety Analyses

Safety and tolerability endpoints will be summarized descriptively, based on the FAS. These summaries will be made in several ways in consideration of the varying durations of treatments: (1) for all subjects across the entire study; (2) by an appropriately chosen time segment, depending on the duration of therapy, e.g., by 3-, 6-, or 12-month intervals from start of therapy; and (3) by rates per patient year (i.e., %/year) or month.

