- 4. Subject has consented to provide tumor slides (or tumor tissue blocks) for biomarker evaluation. Before enrolment the site must confirm the availability of the tumor sample. If there is no sample available, the trial chair must be contacted for approval. If enrolment in the treatment portion of the study has taken place based on HRAS mutant status as assessed using a blood sample, tumor tissue must be sent before starting cycle 2 of treatment, and It will be used in part for confirmation of HRAS mutant tumor status. Confirmation of HRAS mutant status in tumor tissue is required for continuation of treatment. If HRAS mutant is not confirmed in tumor but is clearly positive in blood, the trial chair will be contacted for approval and the treatment could be maintained. All treated subjects will be evaluated for safety.
- 5. Subject has measurable disease according to RECIST v1.1.
- 6. At least 2 weeks since the last systemic therapy regimen prior to enrolment. Subjects must have recovered to NCI CTCAE v. 4.03 < Grade 2 from all acute toxicities (excluding Grade 2 toxicities that are not considered a safety risk by the Sponsor and Investigator) or toxicity must be deemed irreversible by the Investigator.

- 7. At least 2 weeks since last radiotherapy. If radiation was localized to the only site of measurable disease, there must be documentation of disease progression of the irradiated site. Subjects must have recovered from all acute toxicities from radiotherapy. Subjects may be on a daily dose of corticosteroids (≤ 20mg prednisone or equivalent), as part of their management from prior radiotherapy.
- 8. ECOG performance status of 0 or 1.
- 9. Acceptable liver function:
 - a. Bilirubin \leq 1.5 times upper limit of normal (x ULN); does not apply to subjects with Gilbert's syndrome diagnosed as per institutional guidelines.
 - b. AST (SGOT) and ALT (SGPT) \leq 3 x ULN; if liver metastases are present, then \leq 5 x ULN is allowed.
- 10. Acceptable renal function with serum creatinine \leq 1.5 x ULN or a calculated creatinine clearance \geq 60 mL/min using the Cockcroft-Gault or MDRD formulas.
- 11. Acceptable hematologic status:
 - a. ANC \geq 1000 cells/µL.

- b. Platelet count \geq 75,000/µL.
- c. Hemoglobin \ge 9.0 g/dL.
- 12. Female subjects must be:
 - a. Of non-child-bearing potential (surgically sterilized or at least 2 years postmenopausal); or

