7.4 Removal of Subjects from Treatment or Assessment

Subjects may withdraw their consent to participate in this study at any time without prejudice. The Investigator must withdraw from the study any subject who requests to be withdrawn. A subject's participation in the study may also be discontinued at any time at the discretion of the Investigator and in accordance with his/her clinical judgment. Every effort should be made to complete, whenever possible, the tests and evaluations listed for the End of Treatment visit. The Sponsor must be notified of all subject withdrawals as soon as possible. The Sponsor also reserves the right to discontinue the study at any time for either clinical research or administrative reasons and to discontinue participation by an individual Investigator or site for poor enrolment or noncompliance.

Overall, the reasons for which the Investigator or Sponsor may withdraw a subject from study treatment include, but are not limited to, the following:

- Subject experiences disease progression
- Subject experiences unacceptable toxicity
- Subject requires more than 2 dose reductions
- Subject experiences toxicity that is deemed by the Investigator to be no longer safe for the subject to continue therapy
- Subject requests to withdraw from the study treatment
- Subject requires or has taken medication prohibited by the protocol
- Subject is unwilling or unable to comply with the study requirements
- Subject withdraws consent to collect health information
- Subject was erroneously admitted into the study or does not meet entry criteria
- Subject is lost to follow-up
- Subject becomes pregnant

Subjects will return for an End of Treatment visit within approximately 30 days after the last administration of the study drug (or sooner if another anticancer therapy is to be initiated). If a subject fails to return for scheduled visits, a documented effort must be made to determine the reason. If the subject cannot be reached by telephone after 2 attempts, a certified letter should be sent to the subject (or the subject's legally authorized representative, if appropriate) requesting contact with the Investigator. This information should be recorded in the study records.

The Investigator must obtain documented consent from each potential subject prior to participating in a clinical trial. This trial has two consents forms, one per pre-screening phase and another per treatment phase.

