9.1 Efficacy Variables

Radiological and/or physical assessments of the tumor lesions will be made at screening (4 weeks before the first study drug administration), and approximately every 8 weeks for the first 6 months (cycles 2, 4, 6) and then every 12 weeks (cycles 9, 12, 15, etc.) until disease progression, starting at the end of Cycle 2. Additional tumor assessments may be conducted if deemed necessary by the Investigator or for a confirmation of an objective response. Subjects who discontinue treatment for reasons other than disease progression must continue tumor assessments until disease progression, withdrawal of their consent to study procedures or initiation of another anticancer therapy. Efficacy assessments may also be conducted at treatment discontinuation (End of Treatment visit) if the reason for the treatment termination is other than disease progression and a tumor assessment was not done within 8 weeks before

treatment discontinuation (assessment must be conducted before additional anti-tumor therapy is started). Scans at the End of Treatment visit will be also conducted if required to confirm response to treatment.

Lesions to be included in the tumor assessments should follow RECIST v1.1 criteria (Appendix II). Spiral CT scan with a contrast agent is the preferred imaging method. Tumor assessment with spiral CT scans of the abdomen, pelvis and chest plus other relevant evaluations, e.g. bone scans, should be performed as appropriate. Subjects with contrast allergy may use non-contrast CT or MRI, whichever is required to adequately assess all disease.

Objective response (complete response and partial response) as determined by the subject's best tumor response, duration of response, and time to progression will be assessed using RECIST criteria version 1.1. Confirmation of response is required.

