11.1 Populations

11.1.1 Efficacy Analysis

The FAS population will serve as the primary population for the analysis of tumor response and other efficacy-related data. Subjects will be excluded for FAS for the following reasons:

- No baseline data
- Failure to receive at least one dose of tipifarnib
- No post-baseline endpoint data subsequent to at least 1 dose of study drug

A supportive analysis using the Per-Protocol population will be performed for the tumor response analysis. The Per-Protocol population excludes subjects due to important deviations from the protocol that may substantially affect the results of the primary analysis, such as not taking at least 80% of the intended dose in cycle 1. The final determination on protocol violations, and thereby the composition of the Per-Protocol population, will be made prior to locking the clinical database and final analysis and will be documented in a separate memorandum.

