11.1.2 Safety Analysis

The All Subjects as Treated (ASaT) population will be used for the analysis of safety data. The ASaT population consists of all enrolled subjects who receive at least one dose of tipifarnib. At least one laboratory or vital sign measurement obtained subsequent to at least one dose of study drug is required for inclusion in the analysis of a specific safety parameter. To assess change from baseline, a baseline measurement is also required.

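### Section 11.2.2.3 puts the safety summaries on the FAS, while section 11.1.2 assigns safety data to the ASaT population

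*Combined protocol and SAP*

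**What the plan says.** Three parts of the combined protocol and SAP bear on who is counted in the safety tables.

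- **Section 11.1.2 (Safety Analysis):** "The All Subjects as Treated (ASaT) population will be used for the analysis of safety data". It continues: "The ASaT population consists of all enrolled subjects who receive at least one dose of tipifarnib". A post-dose laboratory or vital sign value is needed only for the particular parameter being analysed.
- **Section 11.2.2.3 (Safety Analyses):** "Safety and tolerability endpoints will be summarized descriptively, based on the FAS".
- **Treatment-phase inclusion criterion 4 (Synopsis and section 6.1.2):** "All treated subjects will be evaluated for safety".

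The FAS is defined in section 11.1.1, headed Efficacy Analysis: "The FAS population will serve as the primary population for the analysis of tumor response and other efficacy-related data". Three reasons remove a subject from it: no baseline data, no dose taken, and "No post-baseline endpoint data subsequent to at least 1 dose of study drug".

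**The concern.** Sections 11.1.2 and 11.2.2.3 govern the same output and give it different denominators. The document does not say that the FAS summaries are additional to ASaT summaries, or that the two sets are meant to coincide.

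Safety and tolerability is Secondary Objective 2. A programmer who follows section 11.2.2.3 literally could leave out treated subjects whose adverse events were properly collected under sections 9.8 and 9.9. In addition, the ASaT appears in the available text only in the abbreviations list and section 11.1.2. If section 11.2.2.3 prevails, the population created for safety is not used for the safety summaries.

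**Working it through.** The plan gives no figure to reproduce here. The check compares the two definitions, then asks whether a dosed subject could fall between them and how much one such subject would weigh.

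**1. Compare the definitions (sections 11.1.1 and 11.1.2).**

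| Condition | In the ASaT? | In the FAS? |
|---|---|---|
| Not dosed | No | No |
| Dosed, no baseline data | Yes | No |
| Dosed, no post-baseline endpoint data | Yes | No |
| Dosed, with both | Yes | Yes |

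The FAS is therefore a subset of the ASaT. The two are equal only if the second and third rows are empty. The per-parameter condition on laboratory and vital sign values does not make the ASaT into the FAS, because it does not remove a subject from the population.

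**2. Can the third row be occupied?** Section 7.3 sets 28-day cycles and section 9.1 puts the first scheduled post-baseline scan at the end of Cycle 2:

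2 cycles × 28 days = 56 days.

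During that period a dosed subject may have no post-baseline tumor data. Section 7.4 says: "Subjects may withdraw their consent to participate in this study at any time without prejudice". Under section 9.1, subjects who stop treatment without progression "must continue tumor assessments until disease progression, withdrawal of their consent to study procedures or initiation of another anticancer therapy". Two routes out follow:

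- Withdrawal of consent before the first scan.
- Start of another anticancer therapy before the first scan. Section 9.1 permits an End of Treatment scan before the new therapy, but does not require one.

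Stopping for toxicity alone should not remove a subject, because scans continue.

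**3. The result depends on what endpoint data means.** The plan does not define the term.

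- Tumor response data only: subjects who leave before any post-baseline scan drop out of the FAS.
- Also PFS (section 5.3), assuming death counts as an event: early deaths stay in, but early withdrawals can still drop out.
- Also TEAEs and SAEs (Secondary Endpoint 2, section 5.2): few or none drop out on this ground.

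The exclusion for no baseline data applies under every reading.

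**4. Weight of one omitted subject.** The Synopsis definition of an evaluable subject requires at least two doses of tipifarnib. Every evaluable subject is therefore in the ASaT, and the ASaT is at least as large as the evaluable number. One omitted subject is then at most:

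- 1/18 = 5.6% of the ASaT if 18 evaluable subjects are reached;
- 1/7 = 14.3% if the trial stops after the 7 evaluable subjects of stage 1.

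These are upper limits per subject. They do not estimate how many would be lost. The documents give no basis for a shift in event rates, so none is calculated.

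**The case against.** The strongest reply is that the two sets may be the same in practice. The protocol itself uses the word endpoint for safety: section 11.2.2.3 does so, section 5.2 lists TEAEs and SAEs as an endpoint, and Safety and Tolerability sits under the section 11.2 heading, Endpoints. On that reading, any dosed subject with a post-dose safety record stays in the FAS. The exclusion for no baseline data should also be nearly empty, because entry requires measurable disease, performance status and laboratory values. Moreover, section 11.1.2 is explicit and section 11.1.1 ties the FAS to efficacy, so a careful analyst would probably choose the ASaT anyway. The summaries are only descriptive, and section 11 leaves details of key secondary analyses to a SAP.

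The sentence on evaluating all treated subjects is also weaker support than it may look. It closes inclusion criterion 4, after text on subjects enrolled from a blood result, and names no analysis set.

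Most of this stands as a limit on size. The loss may be zero, and the inclusion-criterion sentence supports the ASaT reading without being a second, independent contradiction. It does not remove the conflict. The exclusion in question sits under the heading Efficacy Analysis, where endpoint data can fairly be read as tumor data. Whoever writes the SAP details would still face two opposing instructions that the available text does not resolve.

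**Conclusion.** The concern holds. Sections 11.1.2 and 11.2.2.3 contradict each other on the safety population, and the reference to the FAS in section 11.2.2.3 is wrong as written. That the ASaT is intended is an inference, but a strong one: it is the population defined for safety, the FAS is defined for efficacy, and inclusion criterion 4 agrees with the ASaT rule.

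Confidence in the textual conflict is high. The practical size is uncertain: anywhere from no subjects to a few, depending on how endpoint data is read and on whether anyone leaves before the first scan at about 56 days. No bias in event rates is claimed. The matter should be fixed because it concerns a secondary objective in a small trial and costs almost nothing to correct.

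**What to change.** In section 11.2.2.3, replace the FAS with the ASaT population as the basis for the safety and tolerability summaries, with a cross-reference to section 11.1.2. The cost is one phrase.

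While editing, note that section 11.2.2.2 (Concurrent Medications), under the same Safety and Tolerability heading, uses the FAS and PPS. The proposed change does not touch it, so denominators within section 11.2.2 will differ and tables should state their population.

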11.2.2.4 Demographic and Baseline Characteristics

Demographic and baseline characteristics will be summarized across all subjects in the FAS, and across all subjects in the PPS. Continuous endpoints will be summarized by n, mean, median, minimum, maximum, and standard deviation. Categorical endpoints (includes binary endpoints) will be summarized by counts and percents per category.

11.3 Sample Size Determination

No statistical testing is planned for the pre-screening phase. The sample size was determined based on the expected frequency of HRAS mutations in SQ-NSCLC (2%). In order to identify up to 18 evaluable subjects that could enroll into the treatment phase, approximately 2000 subjects will be enrolled in the pre-screening phase.

Up to 18 evaluable subjects will be enrolled in the treatment phase using a two-stage design (Simon, 1989). Seven evaluable study subjects will be enrolled for the first stage; the study will

be terminated if 0 responses are observed at end of first stage. Otherwise, an additional 11 subjects will be enrolled for the second stage.

At the completion of two-stage study, the study is considered as failure if there are 3 or less responses out of 18 evaluable subjects, indicating the true ORR is 10% or less. If there are 4 or more responses, the treatment will be considered of further interest indicating the true ORR is higher than 10%.

For this two-stage study design, a null response rate of 10% and alternative response rate of 30% are assumed. It provides 80% power to detect a difference between 10% and 30% ORR at one-sided significance level of 0.089. Using this design, the probability of terminating the study at the end of first stage is 0.48 if the true ORR is 10% or less while the probability of terminating the study at the study at the end of first stage is 0.13 if the true ORR is 30%.

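### The stated chance of stopping after stage 1 at a true ORR of 30% is 0.13, but the 0-of-7 rule gives 0.082

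*Combined protocol and SAP*

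**What the plan says.** Section 11.3 and the Statistical Methods part of the Synopsis describe the same design.

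- **Stage 1:** "Seven evaluable study subjects will be enrolled for the first stage", and the study is to "be terminated if 0 responses are observed at end of first stage".
- **Stage 2:** if the study does not stop, "an additional 11 subjects will be enrolled for the second stage".
- **Final rule:** "the study is considered as failure if there are 3 or less responses out of 18 evaluable subjects"; four or more responses count as success.
- **Hypotheses:** "a null response rate of 10% and alternative response rate of 30% are assumed".
- **Error rates:** "It provides 80% power to detect a difference between 10% and 30% ORR at one-sided significance level of 0.089".
- **Early stopping under the null:** "end of first stage is 0.48 if the true ORR is 10% or less".
- **Early stopping under the alternative:** "end of first stage is 0.13 if the true ORR is 30" per cent.

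The last figure is the one at issue. It has the same value in both sections.

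**The concern.** The stage 1 rule has one way to stop: no responses among seven subjects. Its stopping probability at any true ORR p is (1 − p)^7, with nothing else to choose or assume. At p = 0.30 this is well below 0.13, and the gap is too large for rounding.

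This is the plan's only figure for the chance that the futility rule ends the study after seven subjects although tipifarnib has the targeted activity. A sponsor, investigator or ethics committee weighing that rule would look to it. It also stands beside a power figure quoted at the same 30% ORR, and the two do not belong to the same design. Someone checking the design will find the mismatch and may then doubt the figures that are correct. Uncorrected, the value can be carried into later study documents.

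**Working it through.** **Inputs, all from section 11.3:** stage 1 n = 7, stop on 0 responses; stage 2 n = 11, total 18; success needs at least 4 of 18; null ORR 0.10, alternative ORR 0.30.

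**Formulas.** Let X1 be the responses in stage 1 and X2 those in stage 2, both binomial with true ORR p.

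- Probability of early stopping: PET(p) = P(X1 = 0) = (1 − p)^7.
- Probability of success: P(X1 = 1)·P(X2 ≥ 3) + P(X1 = 2)·P(X2 ≥ 2) + P(X1 = 3)·P(X2 ≥ 1) + P(X1 ≥ 4).

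**Step 1: figures that reproduce.**

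- PET at 10%: 0.9^7 = 0.4783 (stated 0.48).
- Alpha, p = 0.10: 0.3720 × 0.0896 + 0.1240 × 0.3026 + 0.0230 × 0.6862 + 0.0027 = 0.0893 (stated 0.089).
- Power, p = 0.30: 0.2471 × 0.6873 + 0.3177 × 0.8870 + 0.2269 × 0.9802 + 0.1260 = 0.8000 (stated 80%).

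**Step 2: the disputed figure.**

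- PET at 30%: 0.7^7 = 0.0824 (stated 0.13).
- Absolute difference: 0.130 − 0.082 = 0.048. Ratio: 0.13 / 0.0824 = 1.58.

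**Step 3: could 0.13 be right under another reading?**

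| Reading | Value at ORR 30% |
|---|---|
| Stop on 0 of 5 | 0.168 |
| Stop on 0 of 6 | 0.118 |
| Stop on 0 of 7 (as stated) | 0.082 |
| Stop on at most 1 of 7 | 0.329 |
| Stop on at most 1 of 10 | 0.149 |
| Stop on at most 1 of 11 | 0.113 |
| Overall probability of failure, both stages | 0.200 |

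None of these is 0.13. Among all stage 1 rules with up to 18 subjects, only stopping on at most 2 of 15 rounds to 0.13 at an ORR of 30%. That rule would stop with probability 0.82 at an ORR of 10%, which contradicts the stated 0.48.

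**Step 4: which ORR would give 0.13?** Solving (1 − p)^7 = 0.13 gives p = 0.253; for example, 0.75^7 = 0.1335. The figure would fit a true ORR of about 25%, a rate that the plan does not use.

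**Step 5: place in the type II error.** At 30% the design fails with probability 0.200. Of this, 0.082 comes from trials that stop at stage 1 and 0.200 − 0.082 = 0.118 from trials that go on and end with 3 or fewer responses. The stated 0.13 would imply a split of 0.13 and 0.07.

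**The case against.** No one disputes the arithmetic; the case on the other side is about weight.

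- **Nothing depends on the figure.** No rule, sample size or analysis takes 0.13 as an input, and the plan does not say that the interim rule was chosen on it. It is a descriptive property reported after the design is fixed. This stands.
- **The error is on the cautious side.** The risk of wrongly stopping is 8.2%, not 13%, so anyone who accepted the rule at 13% would accept it at 8%. This also stands: no subject, decision or inference is harmed.
- **The 8.2 points are not the power cost of the interim look.** Many trials with 0 of 7 would fail anyway. After 0 of 7, success would need at least 4 of 11, which has probability about 0.43 at an ORR of 30%. The look therefore costs about 0.0824 × 0.43 = 0.035. This agrees with the single-stage comparison: 18 subjects with the same cut-off have power 0.8354, and 0.8354 − 0.8000 = 0.035. The 8.2 points are a partition of the failures and should be read only as that.
- **The 25% origin is a guess.** The documents name only 10% and 30%, so the match shows where the number might have come from and no more.
- **It is one error.** The Synopsis repeats section 11.3, and the repetition adds no weight.

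These points limit the consequences. None of them makes 0.13 a property of the stated design.

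**Conclusion.** The concern holds. Under the stated stage 1 rule the probability of stopping at a true ORR of 30% is 0.082; the plan's 0.13 is wrong. The result assumes only independent responses with a common probability, the same binomial model that reproduces the plan's alpha, power and null stopping probability.

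The design itself is sound. In a search of two-stage designs for 10% versus 30% with alpha at most 0.10 and power at least 80%, 0/7 followed by 3/18 has the smallest expected sample size under the null (12.7) and no design has a smaller total. The fault is confined to one reported operating characteristic. It should be corrected, but it is not a defect in the trial's conduct or its inference.

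**What to change.** Replace 0.13 with 0.08 (0.082 to three decimals) as the stage 1 stopping probability at a 30% ORR, in section 11.3 and in the Statistical Methods part of the Synopsis. If the authors did mean to show a 25% scenario, they should label it as 25%, where 0.13 is correct, and give 0.08 for 30% beside it. Any later document that quotes the operating characteristics should carry the corrected value.

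The cost is a text edit in two places. The sample size, stopping rule, final cut-off, alpha and power stay as they are.
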